6.3.3. Demographics and Baseline Characteristics

Demographic/baseline characteristics collected at the Screening/Day 1 visit will be summarized and presented for each treatment group. Descriptive statistics will be presented for the continuous variables. Frequency counts and percentages will be presented for the categorical variables for each category. The following variables will be presented:

- Demographic characteristics (*Screening*)
 - Age (years)
 - Sex (male, female)
 - Race
 - Ethnicity
 - Height (cm)
 - Weight (kg)
 - BMI (kg/m²)
- Vulvovaginal Examination (*Screening*)
- QOL questionnaire (*Day 1*)
- Fertility Status

- Surgically Sterile / Infertile
- Post-Menopausal
- Potentially Able to Bear Children
- Method of Birth Control
 - Oral Contraceptives
 - Depo Contraceptives (Implants / Injectables)

6.3.4. Medical History

Medical history terms will be coded using the Medical Dictionary for Regulatory Activities (MedDRA 26.0) dictionary. All the medical history will be summarized by system organ class (SOC) term and preferred term for each cohort by treatment group. For subjects with the same SOC and preferred term occurring more than once, the first occurrence will be tabulated. Medical history events will be sorted alphabetically by SOC and within each SOC, the PT will be presented by decreasing order of total frequencies.

Conditions will be listed, including the verbatim investigator description of the relevant medical condition, the coded terms (SOC, preferred term), start date, end date, and whether the condition is ongoing.

6.3.5. Prior and Concomitant Medications

Prior medications are defined as any medication started and discontinued prior to the first dose of study treatment. Concomitant medications are defined as any medication taken on or after the first dose of study treatment, including those who started prior to the date of the first dose of study treatment and continued past that date. See [section 7.1.3](#) for handling of completely or partially missing dates for prior and concomitant medications.

6.3.6. Study Drug Administration

Treatment Cycle 1: All randomized subjects

Subjects who meet all the inclusion and none of the exclusion criteria will be randomized to treatment and stratified into 2 groups based on the Candida species and presence or absence of underlying conditions. Subjects will receive open-label oral ibrexafungerp 300 mg BID for one, three or seven consecutive days per [TABLE 1](#):

| Treatment Group | Criteria | Ibrexafungerp Dose Randomization and Stratification |
|-----------------|---|---|
| Group A | Subjects without underlying medical conditions AND known to have isolates other than C glabrata, C krusei, C auris | 1 Day dosing (300mg AM and 300mg PM) N = 50 |
| Group B | Subjects with underlying medical conditions: DM, immunocompromised conditions (e.g. HIV), debilitation, immunosuppressive therapy (e.g. corticosteroids), recurrent VVC (≥ 3 episodes/year) AND/OR known to have C glabrata, C krusei or C auris isolates | 3 Days or 7 Days dosing (300mg AM and 300mg PM) Randomized 1:1 N = 50:50 |

6.4. Efficacy Analyses Cycle 1

The efficacy analyses will be conducted using the MITT (primary analysis population), ITT and PP populations to evaluate ibrexafungerp. Efficacy outcomes will be presented by treatment group in Cycle 1.

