Three (3) subjects reported SAEs during the study: 2 SAEs were reported by 1 subject (0.4%) who received ibrexafungerp (pneumonia and bronchial hyperreactivity), and 2 SAEs were reported by 2 subjects (1.6%) who received placebo (diabetes mellitus and hypokalemia); none were considered to be related to the study drug.

A total of 5 subjects in the ibrexafungerp group experienced TEAEs that resulted in discontinuation. Of these, 2 subjects experienced TEAEs leading to withdrawal of the study drug and discontinuation from the study (vomiting and dizziness). In addition, 3 subjects experienced

TEAEs leading to discontinuation after completing study treatment (bacterial vaginosis and vulvovaginal itching; not related to study drug). There were no deaths reported during the study.

Mean clinical laboratory results and vital sign measurements observed at the TOC visit were generally similar to those observed at baseline, with no notable differences between treatment groups.

SCY-078-306, A Phase 3, Multicenter, Randomized, Double-Blind, Placebo-Controlled Study to Evaluate the Efficacy and Safety of Oral Ibrexafungerp (SCY-078) vs. Placebo in Subjects with Acute Vulvovaginal Candidiasis

A total of 455 subjects were enrolled, and 449 subjects received at least 1 dose of randomized study drug, 298 subjects received ibrexafungerp and 151 subjects received placebo.

The primary objective was to evaluate the efficacy of oral ibrexafungerp versus placebo in female subjects 12 years and older with VVC by comparing the clinical outcomes of ibrexafungerp and placebo. Efficacy was defined as the percentage of subjects with clinical cure (complete resolution of signs and symptoms) at the TOC visit. The primary analysis was conducted using the Modified Intent-to-Treat (mITT) set, which included 272 randomized subjects (188 subjects in the ibrexafungerp group and 84 subjects in the placebo group) who had a diagnosis of symptomatic AVVC and a positive culture for *Candida* species at baseline. The study achieved the primary endpoint reaching statistical significance. Overall, the percentage of subjects with clinical cure at the TOC visit in the mITT set was statistically significantly higher for the ibrexafungerp group than the placebo group (63.3% versus 44.0%; P=0.007).

Ibrexafungerp was generally well-tolerated by subjects with AVVC when administered as a 300-mg oral tablet BID for 1 day.

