4.2.2. Secondary Endpoints

Efficacy as measured by:

- The percentage of subjects with clinical improvement:
 - Total composite score of 2 on the VSS scale at the TOC and FU visits
 - Total composite score of 1 on the VSS scale at the TOC and FU visits.
- The percentage of subjects with total composite score equal or less than 2 and equal or less than 1 on the VSS scale at the TOC and FU visits.
- The percentage of subjects with clinical success (at least 50% reduction from baseline in the total composite VSS score) with no additional antifungal therapy required based on investigator's judgment) at the TOC and FU visits.
- The percentage of subjects with mycological response (defined as a negative culture for growth of *Candida spp.* or subject is asymptomatic, therefore culture not done) at the TOC and FU visits.
- The percentage of subjects with both clinical cure and mycological response at the TOC and FU visits.
- The percentage of subjects with clinical cure at the FU visits.
- The absolute change in total composite VSS score from baseline to the TOC and FU visits.

Exploratory Endpoints:

- Absolute improvement in QOL outcomes at TOC and FU visits compared to baseline as measured by QOL survey.
- Subjects whose signs and symptoms have resolved enough that additional antifungal treatment was not required based on clinical judgement.
- Time to resolution of symptoms.

Safety and Tolerability as measured by:

Adverse events (AEs), vital signs, treatment discontinuation, and safety laboratory tests.

5. Study Design

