6.2. Analysis Populations

The study populations to be used in the analyses are defined as follows:

Intent-to-Treat (ITT) Population: All ibrexafungerp-treated subjects.

Modified Intent-to-Treat (MITT) Population: All treated subjects who have a positive culture for *Candida* species at Screening.

Per-Protocol (PP) Population: All MITT subjects who have completed the study drug treatment, who did not have major protocol deviations likely to affect study efficacy AND who have a TOC evaluation.

Safety Population: All enrolled subjects who received at least one dose of study drug.

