6.4.2. Secondary Efficacy Analyses

6.4.2.1. Definition of Secondary Endpoint

The following treatment outcome definitions will be used for the assessment of efficacy relative to baseline: Clinical Outcome.

- Clinical Cure: Complete resolution of signs and symptoms with total composite score of 0 on the VSS Scale and with no additional antifungal therapy required based on investigator's judgment.
- Clinical Improvement: Partial resolution of signs and symptoms with total composite score of 1 or 2 on the VSS Scale and with no additional antifungal therapy required based on investigator's judgement.
- Clinical Success: At least 50% reduction from Baseline in the total composite VSS score with no additional antifungal therapy required based on investigator's judgment .
- Clinical Failure: Persistence and/or worsening of signs and symptoms or need for additional antifungal therapy (this definition also applies to cycle 2 patients).

The following mycological outcome definitions will be used for the assessment of subjects with mycological response.

- Mycological Eradication: Negative culture for growth of *Candida* species .
- Presumed Eradication: Subject is asymptomatic, therefore cultures not done .
- Mycological Persistence: Positive culture for growth of *Candida* species.

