6.4.2.2. Main Analysis Approach

Frequency and percentage of subjects with total composite score equal or less than 2 on the VSS scale at the TOC and FU visits, and total composite score equal or less than 1 on the VSS scale at the TOC and FU visits will be summarized.

Frequency and percentage of subjects with clinical improvement, clinical success, mycological response, with both clinical cure and mycological response at TOC and FU visit, with clinical cure at FU visit will be summarized.

The value and absolute change in total composite VSS score from baseline to the TOC and FU visits will be summarized with descriptive statistics.

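### The ITT tables count women without a positive Screening culture as possible mycological responders, which probably inflates the ITT mycological rate

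*SAP*

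**What the plan says.** SAP 6.4 sets the populations for all efficacy analyses: "The efficacy analyses will be conducted using the MITT (primary analysis population), ITT and PP populations to evaluate ibrexafungerp". Protocol 18.6.2 matches it. SAP 6.2 defines the sets. For ITT it reads "Intent-to-Treat (ITT) Population: All ibrexafungerp-treated subjects". The modified set (MITT) is "All treated subjects who have a positive culture for" Candida at Screening, and the per-protocol (PP) set lies within MITT.

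SAP 4.2.2 gives the endpoint as "The percentage of subjects with mycological response (defined as a negative culture for growth of" Candida, "or subject is asymptomatic, therefore culture not done) at the TOC and FU visits". SAP 6.4.2.1 defines eradication in the same way: "Mycological Eradication: Negative culture for growth of" Candida. Neither mentions the Screening culture. SAP 6.4.2.2 then plans "Frequency and percentage of subjects with clinical improvement, clinical success, mycological response, with both clinical cure and mycological response at TOC and FU visit", with no restricted denominator and no category for women who cannot be assessed. SAP 6.5.1 carries the secondary analyses over to Cycle 2 unchanged.

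**The concern.** Mycological response is meant to show that the drug cleared the organism. That can be shown only in a woman whose organism grew before treatment. Applied to ITT, the definition also credits a woman whose culture was negative before the first dose and is negative afterwards.

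Such women can be enrolled. Protocol 11.1 and 14.10 require a positive KOH smear. The culture goes to a central laboratory, and Screening and Baseline may fall on the same day, so dosing can precede the culture result. A separate MITT set implies that the plan expects them.

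At stake is the meaning of the ITT mycological rate, and of the ITT rate for clinical cure combined with mycological response. The mycological rate would mix two kinds of women and would probably look better than the rate in women with proven infection. For a woman who stays culture-negative, the combined endpoint reduces to clinical cure alone.

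**Working it through.** **No figure to reproduce.** The plan has no formal sample size calculation and states no mycological response rate. The check is of the definitions, followed by a sensitivity range.

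**Step 1: follow one woman through the rules.** She is KOH-positive, has a negative Screening culture and is treated. She is in ITT but not in MITT or PP. Culture is scheduled for everyone at the test-of-cure visit and at 14 days after end of treatment (Protocol 14.10 and Table 1). If it is negative, she is a responder. At the later follow-up visits culture is taken only if there are symptoms, so being asymptomatic is enough. If a culture is positive, she is classed as persistence.

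**Step 2: formula.** Let f be the share of ITT without a positive Screening culture, p the response rate in women with one, and q the rate in women without one.

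- ITT rate = (1 − f)p + fq
- Inflation over the culture-positive rate = f(q − p)

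**Step 3: inputs.** The documents give none of the three for this trial.

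- f: assumed 10% to 37%. The upper end is a proxy from study SCY-078-306 in Protocol 7.1.4, whose mITT set is described as one "which included 272 randomized subjects (188 subjects in the ibrexafungerp group and 84 subjects in the placebo group". With 298 women treated with ibrexafungerp, (298 − 188)/298 = 110/298 = 36.9%.
- p: assumed 40% to 70%.
- q: assumed 80% to 100%.

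**Step 4: results** (ITT rate, with inflation in percentage points)

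| f | p = 70%, q = 80% | p = 50%, q = 90% | p = 40%, q = 100% |
|---|---|---|---|
| 10% | 71.0% (+1.0) | 54.0% (+4.0) | 46.0% (+6.0) |
| 20% | 72.0% (+2.0) | 58.0% (+8.0) | 52.0% (+12.0) |
| 36.9% | 73.7% (+3.7) | 64.8% (+14.8) | 62.1% (+22.1) |

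The extremes are 0.10 × (0.80 − 0.70) = +1.0 point and 0.369 × (1.00 − 0.40) = +22.1 points. If q = p the inflation is zero.

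**Step 5: illustration at the planned 150 women.** With f = 36.9%, about 95 women have a positive Screening culture and 55 do not. Let 48 of the 95 respond: 50.5% (Clopper-Pearson 95% CI 40.1% to 60.9%). If 50 of the 55 are also counted (q of about 90%), the ITT figure is 98/150 = 65.3% (57.1% to 72.9%). With the denominator restricted, the figure stays at 48/95 and the inflation is zero.

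**The case against.** The strongest reply is that the design already leads with the right set. MITT requires a positive Screening culture and is the primary analysis population, PP lies within it, and the correct rate will stand beside the ITT figure. The primary endpoint is clinical cure. All of this stands, and it limits the point to supportive tables.

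A reader might infer more than the documents support:

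- **That these women are responders automatically.** They are not. A positive culture at the visit is persistence, and Protocol 18.4 makes a woman without a test-of-cure assessment a treatment failure. Inflation needs q > p, which is likely but not certain.
- **That there was no infection to clear.** Every woman must be symptomatic and KOH-positive, so some negative cultures may be false negatives. What is missing is a positive baseline culture from which eradication can be shown.
- **That about 37% will lack a positive culture here.** That figure comes from acute disease, and that study's mITT set also required a symptomatic diagnosis. In this trial some entry routes and the treatment groups rest on known isolates, so f may differ.
- **That the comparison of 3 with 7 days is compromised.** If f and q were equal in both arms, a difference would shrink by the factor 1 − f, which is 0.631 at f = 36.9%. But the between-arm tests in SAP 6.4.1.2 and 6.4.3.2 cover clinical cure, VSS score and time to resolution. None is planned for mycological response, so only a descriptive contrast is touched.
- **That the same inflation applies to the combined endpoint.** That endpoint still needs a VSS score of 0 and no further antifungal therapy, so the range above cannot be carried over to it.

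The mock tables are in a separate document and might set a denominator. The SAP text does not.

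**Conclusion.** The point holds within those limits. As written, the plan tabulates mycological response and the combined endpoint in ITT with no baseline-culture condition, in Cycle 1 and, through SAP 6.5.1, in Cycle 2. For mycological response the ITT rate is probably too high. The range of about 1 to 22 points rests entirely on the assumed f, p and q, and no narrower figure can be defended from the documents. The primary endpoint and the MITT and PP results are unaffected. It is worth correcting before database lock because the likely direction favours the drug and the correction needs no new data.

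**What to change.** State in SAP 6.4, 6.4.2.2 and 6.5.1 one of the following:

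- mycological response, and clinical cure combined with mycological response, are analysed only in women with a positive Screening culture, that is in MITT and PP; or
- in ITT, women without a positive Screening culture are classed as not evaluable for these two endpoints, and their number is shown.

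Note the departure from Protocol 18.6.2, which lists ITT without exception. Clinical endpoints stay in ITT.

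The cost is a short rule in three places, a recorded departure from the protocol, and a few ITT tables dropped or given a new denominator. The sponsor also gives up an ITT mycological figure that would probably have been the more favourable one.

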6.4.1. Primary Efficacy Analysis

6.4.1.1. Definition of Primary Endpoint

The primary efficacy endpoint is measured by the percentage of subjects with clinical cure (total composite score of 0 on the VSS Scale with no additional antifungal therapy required based on investigator's judgment) at the TOC visit.

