11.4. Early Termination

If the subject experiences persistence or worsening or recurrence of symptoms that per the investigator's assessment (e.g., symptoms ≥ 4) warrant the use of additional antifungal therapy, and the investigator does not consider continuing treatment with ibrexafungerp for a Second Treatment Cycle, a vaginal examination with investigator's rating of signs should be completed. Additionally, vulvovaginal samples should be obtained for KOH testing and pH measurements by the local laboratory, fungal culture by the central laboratory and investigation of other pathogens such as bacterial vaginosis and *Trichomonas vaginalis* by the local laboratory.

If the KOH test is negative, the investigator should consider other causes for the persistence or worsening of the symptoms as additional antifungal medication may not be indicated.

If the investigator's rating of the vulvovaginal signs and vaginal sample collection is not possible prior to the initiation of the additional therapy, it should still be completed as soon as possible after additional therapy is initiated.

In addition to the vaginal examination, the symptoms that led to the use of additional antifungal therapy should be documented in the eCRF and the following procedures should also be completed:

- If additional antifungal therapy is administered prior to or at the TOC visit, all TOC visit procedures should be completed, and no additional visits will be needed. The subject will be considered as early termination due to lack of efficacy prior to or at TOC.
- If additional antifungal therapy is administered after the TOC visit but prior to or at the FU visit, all FU visit procedures should be completed, and no additional visits will be needed. The subject will be considered as early termination due to lack of efficacy after TOC but prior to or at FU.

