18.4. Handling of Missing Data, Dose Adjustments, and Early Withdrawals

For the efficacy analyses, subjects who do not have a TOC assessment will be assigned as treatment failures. For subjects who withdraw from the study early, every effort will be made to collect TOC visit information at the point of withdrawal.

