18.6. Efficacy

18.6.1. Efficacy Assessments

Efficacy assessments will be based on VSS scores, clinical evaluations, QOL outcomes, mycological testing, and additional antifungal use by the TOC visit and FU visits.

18.6.1.1. The following treatment outcome definitions will be used for the assessment of efficacy relative to baseline: Clinical Outcome

- Clinical Cure: Complete resolution of signs and symptoms with total composite score of 0 on the VSS Scale and with no additional antifungal therapy required based on investigator's judgment
- Clinical Improvement: partial resolution of signs and symptoms with total composite score of 1 or 2 on the VSS Scale and with no additional antifungal therapy required based on investigator's judgement.
- Clinical Success: at least 50% reduction from Baseline in the total composite VSS score with no additional antifungal therapy required based on investigator's judgment
- Clinical Failure: Persistence and/or worsening of signs and symptoms or need for additional antifungal therapy

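### Clinical cure tests whether more antifungal therapy is judged to be required, not whether any was taken, so unsanctioned self-treatment with a VSS of 0 at TOC counts as a cure

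*SAP*

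**What the plan says.** The primary endpoint (Protocol 9.1; SAP 4.2.1 and 6.4.1.1) is "total composite score of 0 on the VSS Scale with no additional antifungal therapy required based on" the investigator's judgment, evaluated at TOC. SAP 6.4.2.1 attaches the same condition to clinical improvement and clinical success. Clinical Failure in that section is also worded by need: "Persistence and/or worsening of signs and symptoms or need for additional antifungal therapy".

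Several other places bear on antifungal use:

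- Protocol 18.6.1 lists "additional antifungal use by the TOC visit and FU visits" among the bases of the efficacy assessment.
- Protocol 11.4 covers symptoms that the investigator considers to warrant other antifungal therapy: "If additional antifungal therapy is administered prior to or at the TOC visit, all TOC visit procedures should be completed". It adds: "The subject will be considered as early termination due to lack of efficacy prior to or at TOC".
- Protocol 18.4 sets a failure rule for missing data: "subjects who do not have a TOC assessment will be assigned as treatment failures".
- Protocol 13.2 and Appendix 1 prohibit other antifungals, except as rescue after documented non-response.
- Protocol 13.1 records all medications through TOC, including over-the-counter products, and antifungals through the last visit, with start and stop dates.
- SAP 6.2 and 6.3.2 remove major deviations from PP. The primary population is MITT (SAP 6.4).

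**The concern.** The condition asks for an opinion about need. What could confound the endpoint is a fact: another antifungal taken between first dose and TOC. A woman with no signs or symptoms at TOC will rarely be judged to need more treatment at that moment, so a condition read at the visit adds little to the score itself.

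If she reached VSS 0 after treating herself with another product, the primary rate credits ibrexafungerp with that outcome. The study is open-label, so the judgment is made by someone who knows the regimen. SAP 6.4.1.2 also tests 3 days against 7 days in Group B on this endpoint, so a difference in outside use between those arms would enter the comparison.

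**Working it through.** The documents state no power or sample size calculation, so there is no figure to reproduce. The check has two parts.

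**1. Is there any rule that turns recorded use into non-cure?**

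| Rule | Investigator-directed rescue before TOC | Other use before TOC (e.g. over the counter) |
|---|---|---|
| Cure definition, SAP 6.4.1.1 | Ambiguous: required at some point up to TOC, or still required at TOC | Not caught |
| Clinical Failure, SAP 6.4.2.1 | Fits, since need was judged | Not caught if VSS is 0 and no need is judged |
| Protocol 11.4 | Classed as lack of efficacy, but as a disposition; the SAP does not refer to it | Not addressed: the section starts from therapy the investigator considers warranted |
| Missing-TOC rule, Protocol 18.4 | Not triggered, because TOC procedures are completed | Not triggered |
| Prohibition, Protocol 13.2 and Appendix 1 | Rescue is the permitted exception | A deviation; removes her from PP if judged major, not from MITT or ITT |
| Antifungal use as a basis of efficacy, Protocol 18.6.1 | States an intent; no derivation follows | Same |

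The right-hand column contains no rule that makes the subject a non-cure in the primary analysis. The left-hand column has two texts pointing to failure, but neither is written into the cure derivation. Protocol 11.4 also allows signs to be rated after rescue has begun, so a VSS of 0 after rescue can be recorded.

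**2. What does one reclassified subject do?**

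Inputs: 50 per regimen (SAP 5.4), and cure rates of 50.5% and 63.3% from the two earlier phase 3 studies (Protocol 7.1.4), used only as illustrations. They give 25/50 and 32/50 after rounding. As a smaller MITT I take 30 per regimen. This is an assumption: in study 306, 272 of 449 treated subjects were in the mITT set, 272/449 = 60.6%, and 0.606 × 50 = 30.3.

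Change per subject = 1/n: 1/50 = 2.0 points; 1/30 = 3.3 points.

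Clopper-Pearson 95% limits when k cures are recoded, n = 50:

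| k | From 25/50 | From 32/50 |
|---|---|---|
| 0 | 50.0% (35.5–64.5) | 64.0% (49.2–77.1) |
| 1 | 48.0% (33.7–62.6) | 62.0% (47.2–75.3) |
| 3 | 44.0% (30.0–58.7) | 58.0% (43.2–71.8) |
| 5 | 40.0% (26.4–54.8) | 54.0% (39.3–68.2) |

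Fisher's exact test, 3 days against 7 days, with assumed counts and two cures recoded in the lower arm only:

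- 25/50 v 34/50: p = 0.103; 23/50 v 34/50: p = 0.043.
- 25/50 v 32/50: p = 0.225; 23/50 v 32/50: p = 0.107.

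The values of k and the arm split are hypothetical. The first pair was chosen near the 5% level to show that a few subjects can matter; the second shows that they need not.

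**The case against.** **Rescue is already a failure.** A reader might infer that women rescued by the investigator will be counted as cures. The documents do not support that. Rescue means that need was judged, which meets Clinical Failure, and Protocol 11.4 classes the subject as lack of efficacy. The examination should precede rescue where possible, and the example trigger is a symptom score of 4 or more, so VSS 0 at that assessment is unlikely. This objection stands. What remains for these women is an ambiguity and a missing link in the SAP.

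**Other antifungals are barred.** A reader might also expect frequent systemic antifungal use in Group B, which enrols women with HIV or immunosuppression. But Protocol 11.2 excludes antifungal treatment in the 7 days before Screening and anticipated need for prohibited medication, and Appendix 1 bars other antifungals on study. This limits how often such use should occur. It does not say how it is scored when it does.

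**PP can remove these women.** True if the use is judged a major deviation. PP is not the primary population, and removing a subject is not the same as scoring her as a non-cure.

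**The study is exploratory.** That lowers the stakes, but the cure rate with its interval is still the primary result, and the SAP also attaches a p-value to the Group B comparison.

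**Conclusion.** The point holds in a limited form. For non-rescue use before TOC, the plan as written counts a woman with VSS 0 as a cure in MITT and ITT. For investigator-directed rescue, the protocol points to failure, but the SAP leaves the programmer to decide whether the condition means required at any time up to TOC or still required at TOC.

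The size is 2.0 points of a regimen's cure rate per subject at n = 50, or 3.3 points at an assumed n = 30. The total cannot be stated. The documents give no rate of outside antifungal use, no share of users at VSS 0 and no difference between arms. A reader might turn an assumed usage rate into a bias of several points; nothing in the documents supports such a figure. Even a known count would measure the effect of recoding, not bias, because some of these women might have been cured by ibrexafungerp alone.

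**What to change.** In SAP 6.4.1.1 and 6.4.2.1, state that a subject is not a cure, improvement or success at a visit if either of these holds:

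- a non-study systemic or vaginal antifungal is recorded from the first dose of the cycle being analysed through that visit; or
- the investigator judges additional antifungal therapy to be required.

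Make the rule cycle-specific. For Cycle 1 outcomes, the start of Cycle 2 ibrexafungerp counts as additional antifungal therapy. For Cycle 2 outcomes, Cycle 2 ibrexafungerp is the study drug and does not count. Without this, a rule exempting only Cycle 1 drug would make every Cycle 2 subject a non-cure, because SAP 6.5.1 analyses the Cycle 2 secondary endpoints in the same way as Cycle 1.

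Keep the judgment-only definition as a sensitivity analysis, so that the effect of the rule is visible.

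The cost is SAP wording and one derivation from dated medication records already collected; no new data are needed. There are two downsides. The cure rate may be slightly lower, and an antifungal taken for another indication also counts as non-cure, which is a choice about intercurrent events that the SAP should state openly.
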